Testing of a new Therapeutic Vibration Device to reduce neuromuscular weakness in hospitalized patients.

NCT03479008

Approved 3/2/2020

Testing of a New Therapeutic Vibration Device to Reduce Neuromuscular Weakness in Hospitalized Patients

Principal Investigator: [name], University of Michigan: Department of Emergency Medicine

Objective: Test the ability of axial vibration to produce physiologic, biochemical, and anatomic changes consistent with exercise that would help mitigate the development of myopathy associated with prolonged immobilization.

Specific Aims:

- 1) Phase I: In healthy volunteer subjects, test the ability of low frequency vibration at various frequencies to produce muscle contraction activity, tissue oxygenation changes, oxygen consumption changes (only healthy volunteers), biochemical changes, and anatomical changes consistent with moderate physical activity and favorable effects of vibration.
- 2) Phase II: In critically ill patient subjects, test the ability of low frequency vibration at various frequencies to produce muscle contraction activity, tissue oxygenation, biochemical, and anatomical changes consistent with moderate physical activity and favorable effects of vibration.

Background Information:

During critical illness, patients who are immobilized for more than a few days develop neuromuscular weakness despite receiving full supportive care, which may include physical therapy. In patients requiring mechanical ventilation for longer than 7 days, the incidence of ICU-acquired (neuromuscular) weakness is reported to be between 25% and 60%. Such weakness may contribute to increased duration of mechanical ventilation, increased length of stay in the ICU and hospital, and poor quality of life among survivors. This is part of the newly recognized Post Intensive Care Syndrome (PICS). Moreover, patients who are transferred from the ICU to a high-dependency unit (HDU), intensive therapy unit (ITU), post-operative therapy or outpatient ambulatory care need to be mobile as well as awake for any physical therapy. Patients affected by sepsis, osteoarthritis, spinal cord injury, stroke, multiple sclerosis, cerebral palsy, cancer suffer muscle loss and weakness. Early mobilization (EM) has demonstrated the ability to significantly reduce the detrimental effects of prolonged immobilization such as polyneuropathy and myopathy, which in turn reduces the time patients spend on mechanical ventilation and the overall length of hospital stay. EM treatments include intense physical therapy, cycle ergometry, transcutaneous electrical muscle stimulation (TEMS) and continuous lateral rotational therapy (CLRT). However, scaling of intense physical therapy using therapists is impractical (especially at smaller hospitals) and cannot be implemented in heavily sedated patients. Evidence suggests that whole body vibration may be capable of producing adequate muscle contraction via muscle-spinal loops that may be sufficient to reduce the myopathy and neuropathy of prolonged immobilization thus serving as an effective countermeasure for muscle atrophy.

The purpose of this study is to test a prototype axial vibration device and strategy on its ability to activate large muscle groups, increase muscle blood flow, modulate tissue oxygenation, and increase circulating levels of metabolites associated with exercise/activity. The study will be used to find optimal vibration frequencies that provide maximal signatures associated with muscle and bone stimulation and activity. Eventually we envisage our vibration device to deliver a more effective therapy compared to the incremental gains derived from traditional measures of physical therapy in critically ill patients such

as TEMS, CLRT and cycle ergometry to patients. It may directly benefit the patient in terms of health, length of stay and reduced re-admission, hospital staff in terms of productivity (i.e., through reduction in nursing effort) and the hospital in terms of improved costs/margins and return on investment. Its utility is also envisioned in many other populations of immobilized acutely ill and injured patients as well as those with chronic conditions.

Muscle response and adaptation to vibrating force seems to be influenced by the characteristics of the input signal, i.e., frequency and amplitude, as well as muscle tension [4]. Experiments carried on the muscle-tendon unit have shown that muscle vibration is a strong proprioceptive stimulus that reaches both the primary somatosensory and motor cortices directly and that the frequency exerts a dependent effect on the Ia afferent firing rate that is reflected in differential frequency-dependent effects on corticospinal motor neuron excitability. Thus, the elevated muscle activity during whole body vibration, rely on the level of vibration and explain how the muscle activity in the lower extremity muscles could be dependent on the changes in the accelerations (i.e., the frequency and/or amplitude) delivered by the device [5].

The therapeutic vibration device we have created is based on a unique design, which has not been utilized by any previous commercial vibration therapy device. The device does not experience loss of vibration intensity and provides the flexibility of multi-dimensional parameter adjustments. It is capable of applying force through the axial skeletal spine, through bidirectional compression loading (or prestressing) between the shoulder and the plantar surfaces of the feet. It is placed around the body like a mobile frame so that the applied vibration can affect the whole body. The vibration actuators (drivers) are mobile and can vary in size, frequency response, and force. The design minimizes the possibility of mechanical interference for ventilated/intubated patients.

The device consists of the following parts:

1. Shoulder cups with inner layer of padding
2. Knee braces with inner layer of padding
3. Leg braces with inner layer of padding
4. Axial pre-stressing system using bands and straps from shoulders to legs
5. Vibration actuators (with amplifiers)

[figure not shown]

Figure 1. Therapeutic vibration device

The present prototype shoulder cups are built from Nylon 12 with stiffer inner pad lining at the shoulder interfaces. The leg braces, commercially known as PRAFO® Orthosis is a flagship product of M/s Anatomical Concepts, Inc., with a Polyurethane Foam Pad replaceable liner. The adjustable hinged knee braces are commercial off-the-shelf items, supplied by Mueller Sports Medicine, Inc. The hinges of the braces have been flipped to lock the knee joint to ensure maximum transmission of vibration through the bones axially. The resistance bands are also commercially off the shelf items and provide the necessary prestressing. Prestressing of the modular braces using resistance bands is essential to establish a proper fit and an effective vibration transmission. The actuators are driven by amplifiers, which handle all needed frequencies. The current prototype utilizes different size inertial actuators for different parts of the body. The vibration actuators, commercially known as Butt kicker have been sourced from M/s Guitammer Company. The bigger vibration actuators, mounted on the plantar side of the feet operate in the frequency range of 20 Hz – 40 Hz, as it has been identified as an optimal range for the lower part of the body [1-3]. The smaller vibration actuators mounted on the shoulders provide an excitation frequency in the range of 5 Hz -15 Hz, as the range of 7 Hz - 15 Hz for the upper part of the body is considered optimal [1-3].

Replaceable liners will be used between subjects for both knee braces and shoulder cups/leg braces.

Methodology

The modular structure allows us to target the upper, core, and body in combination. Our experiments test both single actuator applications (single frequency) and multiple actuator (multiple frequency) applications. We will test two protocols to identify the optimal frequencies and amplitudes (intensity of vibration) to achieve optimal physiologic responses consistent with moderate physical activity.

Exclusion Criteria (Phase I and II): Acute spinal cord injury, acute vertebral body fracture or injury, acute stroke or intracerebral hemorrhage, hemodynamic instability or other event/condition believed by the care team to warrant nonparticipation, known pregnancy, prisoner

Phase I (Healthy Subjects):

- 1) Single tone excitation (STE). STE experiments involve vibration of the axial skeleton with a single frequency. During the pilot trials, we will deliver STE therapy to healthy volunteer subjects and measure physiologic changes.
- 2) Multi-Frequency Excitation (MFE). MFE experiments will utilize different frequencies at different amplitudes to upper and lower parts of the body simultaneously to healthy volunteer subjects and measure physiologic changes.

To compare MFE and STE protocols, we will collect data from same subjects for the same duration of 5 minutes over 4-5 matched episodes but will randomize (using simple computer generated randomization table generated by www.randomizer.org) the application of MFE and STE. During these times, mass loading (through adjusting the tension bands) will change to test the effect of loading on the physiologic response to vibration. Subjects will be weighed initially and initial mass loading will match the subject's weight based mass. This loading may be increased to understand if an improved physiologic state is achieved using the measures described below.

The following will be measured:

- 1) Tissue hemoglobin oxygen saturation (StO₂) using near infrared spectroscopy of the thighs, biceps, and brain. This measure will at baseline (prior to each vibration episode), continuously during vibration, and then for 30 minutes after vibration.
- 2) Oxygen consumption (VO₂) using a VO₂ monitor and mask. This measure will at baseline (prior to each vibration episode), continuously during vibration, and then for 30 minutes after vibration.
- 3) Muscle contraction using a noninvasive electromyography (EMG). This measure will at baseline (prior to each vibration episode), continuously during vibration, and then for 30 minutes after vibration.
- 4) Self-selected walking test for recording walking data. The measure will be at baseline. The time required for a subject to walk 10 meters will be recorded and that speed will be selected on the treadmill. The subject will walk for 3 minutes. EMG data will be collected.
- 5) Blood sampling before and after vibration (10 cc's each) may occur to examine markers that are believed to be associated with serum glucose, lipids, inflammatory cytokines (e.g., IL-6, TNF α , IL-1 β), growth hormone, cortisol and bone turnover markers (e.g., C-terminal telopeptide of type I collagen (CTX-I) *and* tartrate-resistant acid phosphatase 5b).

Measures 1-4 above will be made with commercially available devices. Blood assays will be performed in our research laboratories using standard assaying methods.

We anticipated enrolling approximately 50 healthy volunteers.

Phase II (Critically Ill Subjects):

Phase II may begin prior to Phase I completion.

Phase II will consist of trialing optimal loading and frequencies developed in phase I on a targeted population of critically ill or injured subjects who are expected to experience prolonged immobilization in the intensive care unit. Patient subjects may or may not be mechanically ventilated.

These patient subjects will be subjected to a similar series of vibration tuning protocols to maximize physiologic response.

The following will be measured:

- 1) Tissue hemoglobin oxygen saturation (StO₂) using near infrared spectroscopy of the thighs, biceps, and brain. This measure will at baseline (prior to each vibration episode), continuously during vibration, and then for 30 minutes after vibration.
- 2) Muscle contraction using a noninvasive electromyography (EMG). This measure will at baseline (prior to each vibration episode), continuously during vibration, and then for 30 minutes after vibration.

Rectus femoris muscle geometry using Ultrasound as a measure of muscle mass preservation. This measure will be made prior to the first vibration episode and then at the end of the enrollment (5 days later). Blood sampling before and after vibration (10 cc samples) to examine markers that are believed to be associated with serum glucose, lipids, inflammatory cytokines (e.g., IL-6, TNF α , IL-1 β), growth hormone, cortisol and bone turnover markers (e.g., C-terminal telopeptide of type I collagen (CTX-I) *and* tartrate-resistant acid phosphatase 5b).

Measures 1-3 above will be made with commercially available devices. Blood assays will be performed in our research laboratories using standard assaying methods. We will not measure VO₂ on patient subjects due to the complexity of the measure and need for integration into the ventilator circuit.

Patient subjects will be recruited to undergo up to three vibration sessions per day for up to 5 days. Each vibration session is expected to last 5-10 minutes. Blood will be taken prior to the very first vibration session. A second sample of blood will be taken at the end of the last vibration session of the day for each day. A pre-vibration sample will only be obtained on the first day. Thus each patient subject will have a maximum of 5 samples taken during the course of their enrollment.

We anticipated enrolling approximately 50 patient subjects.

Potential Risk and Potential Benefit to the Subjects:

This study is believed to represent minimal risk since whole body vibration platforms are ubiquitous in the their use in the fitness industry and there are several that are FDA approved. None, however are adapted for use for patients immobilized in bed and none have the ability to have their frequencies adjusted.

The potential risks identified with the above project may include the following:

- 1) Transient muscle soreness
- 2) Bruising and discomfort from venipuncture (health volunteers). Blood from patient subjects will be taken from pre-existing intravenous catheters.
- 3) Anemia (patient subjects). We will not obtain blood from patients whose last recorded hemoglobin level is less than 8 mg/dl.
- 4) Breach of confidentiality

The potential benefits identified to the subjects include:

- 1) Knowledge that they are contributing to increasing medical knowledge and to a potential technology that will help mitigate the myopathy associated with prolonged immobility.
- 2) Potential improvement in muscle strength and reduced myopathy (patient subjects).

Statistical Analysis:

Continuous data will be presented as mean (SD) or median (IQR), while categorical data will be presented as percentages. An effect-response analysis will be conducted to describe the effect of changing frequency on the different physiologic responses using a single tone excitation as well as the multi frequency excitation. Effect-response curves will be constructed with the frequencies on the x-axis and the physiologic response on the y-axis. The threshold-effect (desired frequency) will be determined for individual physiologic changes as well as at different combinations.

References/Literature Cited:

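### Phase I aims at responses that resemble moderate activity, but its analysis has no activity comparator or reference level, and VO2 and StO2 are not scheduled during the only activity condition

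*Combined protocol and SAP*

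**What the plan says.** Specific Aim 1 (Phase I, healthy volunteers) looks for muscle contraction, tissue oxygenation and "oxygen consumption changes (only healthy volunteers), biochemical changes, and anatomical changes consistent with moderate physical activity and favorable effects of vibration". The Methodology repeats the standard when it explains why frequencies and amplitudes are varied: "to achieve optimal physiologic responses consistent with moderate physical activity". Specific Aim 2 carries it to patients: "tissue oxygenation, biochemical, and anatomical changes consistent with moderate physical activity and favorable effects of vibration". No section defines moderate activity for any measure.

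The one activity condition is Phase I measure 4: "Self-selected walking test for recording walking data. The measure will be at baseline". The time to walk 10 metres sets the treadmill speed, and then: "The subject will walk for 3 minutes. EMG data will be collected". No other physiologic signal is listed for the walk.

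StO2, VO2 and EMG (Phase I measures 1 to 3) share one schedule: "This measure will at baseline (prior to each vibration episode), continuously during vibration, and then for 30 minutes after vibration". Blood sampling in Phase I is optional and is also placed before and after vibration.

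The comparison named in Phase I is multi-frequency against single-tone excitation in the same subjects, "for the same duration of 5 minutes over 4-5 matched episodes", with loading varied as well. The Statistical Analysis gives summary statistics, curves of response against frequency, and a threshold frequency for each response and for combinations. It does not mention the walk, and it gives no rule that ties the threshold to activity.

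For patients, "Phase II will consist of trialing optimal loading and frequencies developed in phase I". Phase II has no activity condition and does not measure VO2.

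**The concern.** A claim that a response resembles moderate activity concerns its size, so it needs something to be judged against: an activity measured in the same subjects, or a level stated in advance. The plan has neither in its analysis. The highest point on a frequency curve may still lie close to rest, so finding the best setting does not show that it produces an activity-like response.

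The three continuous measures are affected differently. Walking EMG will exist, so an EMG contrast can still be written into the analysis. VO2 during vibration could be judged later against an external level, but a level chosen after seeing the data carries less weight. StO2 has no such route in the documents. If VO2 and StO2 are not recorded during the walk, the direct comparison is lost for both.

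The settings go forward to Phase II under the same wording of the aim. The Phase I walk is therefore the only activity reference in the trial, although healthy volunteers on a treadmill are only an indirect reference for immobilized patients.

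**Working it through.** **Is there a plan figure to reproduce?** No. The only number that bears on Phase I precision is the anticipated enrolment of about 50 volunteers. It comes without alpha, power, effect size or SD, so it cannot be re-derived. The check is mainly of the text.

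**Step 1: comparisons that the text supports in Phase I.** These are vibration against its own pre-episode baseline, multi-frequency against single-tone, across frequencies, and across loadings. None has activity as the comparator.

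**Step 2: measures against conditions (Phase I measures 1 to 5, Phase II, Statistical Analysis).**

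| Measure | Around vibration, Phase I | During walk, Phase I | Planned contrast with walk | Phase II |
|---|---|---|---|---|
| StO2 | yes | no | no | yes |
| VO2 | yes | no | no | no |
| EMG | yes | yes | no | yes |
| Blood markers | optional | no | no | yes |

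Of the three continuous measures, 1 is listed for the walk and 0 have a planned contrast or reference level. Phase II repeats 2 of the 3, with 0 activity conditions.

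**Step 3: recording time, to size the fix.** Take the lower end of the stated episodes, 4, and read the stated 5 minutes as the length of each.
- If the 30 minutes after vibration is counted once: 4 × 5 + 30 = 50 minutes.
- If it follows every episode: 4 × (5 + 30) = 140 minutes.
- VO2 and StO2 minutes during activity: 0.

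Added VO2 and StO2 recording is the existing 3-minute walk plus a rest before it. The documents give no rest length; assume 3 to 5 minutes.
- 3 + 3 = 6 minutes to 3 + 5 = 8 minutes.
- Smallest share: 6/140 = 4.3%. Largest share: 8/50 = 16%.

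Added session time is the rest (3 to 5 minutes) plus recovery before the first vibration baseline (assumed 5 to 10 minutes).
- 3 + 5 = 8 minutes to 5 + 10 = 15 minutes per subject.
- Over 50 subjects: 8 × 50/60 = 6.7 hours to 15 × 50/60 = 12.5 hours.
- Rest alone, which is all the EMG contrast needs at most: 3 × 50/60 = 2.5 hours to 5 × 50/60 = 4.2 hours.

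**Step 4: would the contrast be precise enough to report?** For a paired difference, the 95% half-width in units of the SD of that difference is t(0.975, n − 1)/√n.
- n = 50: 0.284 SD
- n = 40: 0.320 SD
- n = 30: 0.373 SD

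The SD is not in the documents, so no figure in raw units is possible. Estimating the contrast does not by itself call for more subjects.

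**The case against.** The strongest reply is that the aim does not demand a head-to-head comparison. Being consistent with activity can mean the right kind and direction of change, and the Background describes the purpose in that spirit: activate muscle, raise blood flow, and find the frequencies with the strongest signatures. Change from the pre-episode baseline and the frequency curves serve that reading, and they also serve the part of Aim 1 about favorable effects of vibration. This stands. The point is therefore limited to the size of the response.

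A second reply is that the walk does not supply the missing standard, because nothing in the documents calls a self-selected walk moderate. This also stands. It is why the fix includes a stated VO2 level and, failing that, narrower wording of the conclusion. Vibration is also delivered with the knee locked and the body prestressed, so its EMG differs in kind from that of walking. That calls for cautious interpretation but does not remove the value of a reference.

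A third reply is that the walk may not need its own resting recording, since the first pre-vibration rest could serve. It might. The documents give neither the order of the walk and that rest nor the gap between them, so this has to be shown rather than assumed.

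Finally, Phase I is an exploratory tuning study with a one-paragraph analysis, and even the multi-frequency against single-tone comparison has no specified contrast. This limits how serious the point is. It does not answer it, because unrecorded walk data cannot be supplied by later analysis text.

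A reader might go further and infer that Phase I has no comparison at all, or that it cannot meet any reading of its aim. The documents support neither: comparisons between settings and against rest are planned.

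**Conclusion.** The concern holds in this limited form. Followed as written, Phase I can show which way each response moves and which settings move it most, but not whether the size of any response resembles activity. For EMG the gap is in the analysis only. For VO2 and StO2 the walk data are not scheduled and could not be recovered afterwards. The loss is greatest for StO2, since VO2 could still be set against a stated level.

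In size, 1 of 3 continuous measures is listed for the walk, and 0 of 3 have a planned contrast or reference level. The cost figures rest on 4 episodes of 5 minutes each, and on rest and recovery times that are assumptions.

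This is a worthwhile and cheap improvement, not a flaw that makes the trial uninformative. It would be wrong to infer that the walk was meant to represent moderate activity, or that adding it would settle the question for patients. The documents do not say the first, and the walk is only an indirect reference for the second.

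**What to change.** 1. **EMG.** Add to the Statistical Analysis a within-subject contrast, vibration minus walk, each as change from rest, with a 95% interval and identical signal processing (including any filtering) in both conditions. Report it descriptively for every tested setting. This avoids picking the best setting and then estimating on the same data, and it avoids averaging weak settings with strong ones. For the walk's rest, take a short recording before it, or use the first pre-vibration rest if it is shown not to be affected by the walk.
2. **VO2 and StO2.** Where the existing VO2 monitor and near-infrared probes can be used on the treadmill, record both at rest and during the existing walk, in a window fixed in advance. Report the same within-subject differences. Differences are safer than ratios because the net response to vibration may be near zero.
3. **Reference level and wording.** State in advance, with its source, the VO2 level that will count as moderate activity. Otherwise, word conclusions as relative to self-selected walking.

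The cost is analysis text and, if the separate rest is needed, 3-5 minutes per subject for part 1. Parts 1 and 2 together take 8-15 minutes of session time per subject (about 7-12.5 hours over 50), plus set-up. Part 3 needs no new procedure. Other downsides are mask discomfort and possibly altered gait. The documents do not confirm that the equipment works on a treadmill, and whether VO2 levels off within 3 minutes must be checked. Blood markers would still have no activity reference.

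### Phase II blood and 5-day ultrasound changes have no unvibrated reference and cannot show a vibration effect or muscle preservation; comparing frequencies on EMG and StO2 needs a stated order of settings

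*Combined protocol and SAP*

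**What the plan says.** The Objective and the second Specific Aim are causal: the study tests whether vibration can produce physiologic, biochemical and anatomic change. Phase II is one group of about 50 critically ill patients with up to three sessions a day for up to five days. No control, sham or unvibrated period is described.

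The Phase II measures have different reference points:

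- **Blood.** One sample before the very first session, then: "A second sample of blood will be taken at the end of the last vibration session of the day for each day". After day 1 there is no same-day reference: "A pre-vibration sample will only be obtained on the first day". The section concludes: "Thus each patient subject will have a maximum of 5 samples taken during the course of their enrollment".
- **Ultrasound.** "Rectus femoris muscle geometry using Ultrasound as a measure of muscle mass preservation", done before the first episode and again at the end of enrollment, five days on.
- **StO2 and EMG.** "This measure will at baseline (prior to each vibration episode), continuously during vibration, and then for 30 minutes after vibration".

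On settings, Phase II says only that patients receive a series of tuning protocols similar to Phase I. The randomization in the Phase I section concerns multi-frequency against single-tone excitation in healthy volunteers. It does not order individual frequencies.

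Statistical Analysis is descriptive: "Effect-response curves will be constructed with the frequencies on the x-axis and the physiologic response on the y-axis", and "The threshold-effect (desired frequency) will be determined for individual physiologic changes as well as at different combinations". It is not limited to Phase I. It names no comparator, no model and no term for day or episode.

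**The concern.** Background Information says that patients immobilized for more than a few days weaken despite full supportive care. By the plan's own account, then, change without vibration is expected in this population, and calling muscle preserved requires knowing how much would have been lost. Phase II has no such reference for ultrasound or blood. A stable scan could be read as preservation, ordinary wasting as device failure, and a marker trend over five days of intensive care as an effect of vibration.

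Frequency is a separate and narrower matter. If all patients meet the settings in the same order, or settings are chosen according to the patient's condition, frequency is tied to day or illness. The desired frequency could then partly reflect when it was applied.

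**Working it through.** **1. Blood sample count (the one derived figure in the plan).** The schedule gives 1 pre-vibration sample + 1 end-of-day sample × 5 days = 6 samples, or 6 × 10 cc = 60 cc. The stated maximum is 5, or 50 cc. Five results only if the first sample is not counted or at most four days have an end-of-day sample. The plan's figure is not reproduced. The rest of this point does not depend on it.

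**2. Can an overall vibration effect be separated from time?** Assume 50 patients and additive patient and time effects. Count the rank of the design matrix before and after adding a vibration term.

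- Ultrasound, 2 time points: patient + time rank 50 + 2 − 1 = 51; with vibration still 51. Not separable, because every second scan follows vibration.
- Blood, 6 time points: rank 50 + 6 − 1 = 55; with vibration still 55. Not separable. This depends on how time is coded. With five day effects the rank is 54, and vibration raises it to 55 through the day-1 pair. That gain assumes nothing but vibration changes the markers during day 1, although the pair can span three sessions and has no unvibrated reference.
- EMG/StO2, 3 × 5 = 15 episodes, before and during: patient + episode rank 50 + 15 − 1 = 64; with vibration 65. The acute change is separable.

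**3. How misleading could uncontrolled change be?** The documents give no SD or expected change, so the following inputs are assumed. With n = 50, true vibration effect zero and background mean change d in SDs of the change score, the one-sample t statistic has noncentrality d√50 on 49 df, with critical value 2.01.

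| d (assumed) | d√50 | 95% CI excludes zero |
|---|---|---|
| 0.2 | 1.41 | 28% |
| 0.3 | 2.12 | 55% |
| 0.4 | 2.83 | 79% |
| 0.5 | 3.54 | 93% |

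**4. Frequency contrasts on EMG/StO2.** Assume five settings, hence four contrasts, over 15 episodes.

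| Response to vibration | Common order | Random order |
|---|---|---|
| Constant over episodes | 4 of 4 estimable | 4 of 4 |
| Varies by episode (base rank 79) | 0 of 4 | 4 of 4 |

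The per-episode baseline removes background drift. It does not remove a change in responsiveness.

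**5. Measures without a per-episode baseline.** Suppose five settings are given one per day, in the same order to all 50 patients, with no frequency effect and linear drift of b residual SD per day. For b = 0.05, 0.1 and 0.2 (assumed), the last-day setting looks best in about 42%, 62% and 83% of simulated studies (4,000 runs). Chance is 20%, and random order gives 19% to 20%. These figures do not apply to EMG or StO2 change from the episode's own baseline.

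**The case against.** An early, single-group, descriptive device study is legitimate. The analysis section plans summaries and curves, with no interval, test or alpha, so the percentages in step 3 describe a misreading that the plan does not itself commit to. The phrase about muscle mass may only name what ultrasound measures. Random order also sits awkwardly with a phase meant to tune settings for the largest response. All of this stands. It limits the remedy to labelling and assignment and gives no ground for demanding a control arm. The causal wording of the aim remains, and nothing in the plan limits how these two measures will be read.

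Three stronger readings are tempting and are not supported:

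- *A reader might infer that Phase II as a whole is uninterpretable.* EMG and StO2 have a baseline before every episode, and their frequency contrasts survive even a common order if responsiveness is constant.
- *A reader might infer that the frequency curves will be built on blood and ultrasound.* The Objective lists biochemical and anatomic change apart from physiologic change, and the curves are for physiologic responses. On the other side, Background Information seeks frequencies that stimulate bone, and the only bone measures listed are blood markers. Whether blood or ultrasound enters is therefore unclear.
- *A reader might infer that Phase II settings will follow a fixed calendar.* No order is stated at all. A similar series might be meant to carry over the Phase I randomization, but that is not stated, and that randomization does not order individual frequencies.

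**Conclusion.** The point holds in this limited form. Without an unvibrated reference, change in Phase II end-of-day blood markers and in the five-day ultrasound pair cannot support the claim that vibration produced biochemical or anatomic change, or that muscle mass was preserved. The day-1 blood pair does not rescue this. The conclusion follows from the schedule. The 28% to 93% range only illustrates its possible size and rests on assumed background changes.

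Acute EMG and StO2 change is interpretable. Their frequency comparison fails (0 of 4 contrasts against 4 of 4) only if responsiveness varies by episode and all patients share one order; a condition-driven order would tie frequency to illness in a similar way. The missing statement on order leaves that possibility open without establishing it. The change should be made, but it is not a fatal flaw. The count of 6 against 5 samples is a separate inconsistency and adds no weight to the main point.

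**What to change.** 1. In Statistical Analysis, add: *Phase II blood-marker and rectus femoris changes will be reported as uncontrolled change from baseline and will not be interpreted as a vibration effect or as muscle mass preservation. They will not be used to choose the desired frequency unless settings were assigned by randomization (for ultrasound, differing between patients).*
2. In the same section, base the Phase II effect-response curves on EMG and StO2 change from each episode's own baseline, with day or episode in the model. In the Phase II section, randomize the order of the settings tested by the table method already used in Phase I, and log the setting for each session. If order is not randomized, label the Phase II frequency curves exploratory.
3. Reconcile the blood schedule (1 + up to 5 = 6 samples, 60 cc) with the stated maximum (5 samples, 50 cc).

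Items 1 and 2 cost a few sentences and a settings log, with no added blood draws, patients or equipment. The real price is a more modest claim for blood and ultrasound and, if order is randomized, less freedom to tune patient by patient.
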